6.1.10. Active-Control Studies Intended to Show Equivalence

Not applicable to this study.

6.1.11. Examination of Subgroups

Not applicable to this study.

6.2. Disposition of Subjects

The number of subjects included in each analysis population (randomized, ITT, MITT, safety, PP) will be summarized by treatment group. The number of subjects who completed and discontinued (including the reasons for discontinuation) will be summarized for each treatment group.

The ear being treated (Left, Right, Both) will be summarized by treatment group as well as an indication of worse ear if “Both” is selected for the ear being treated.

Subjects who are excluded from an analysis population will be summarized by the reasons for exclusion based on primary reason for exclusion.

6.3. Protocol Deviations

Protocol deviations will not be entered into the database. Deviations leading to exclusion from analysis populations will be identified. Protocol deviations will be presented in a by-subject listing.

6.4. Data Sets Analyzed

Subjects will be summarized based on the primary reason for exclusion. Below is the order to be used in summaries:

6.4.1. Intent-to-Treat (ITT) Population

All subjects who were randomized and dispensed study drug will be included in the ITT population.

6.4.2. Modified Intent-to-Treat (MITT) Population

All subjects in the ITT population with a clinical diagnosis of otomycosis confirmed by positive fungal culture will be included in the MITT population and analyzed according to the treatment group they were randomized. All efficacy analyses will be presented using the MITT population.

6.4.4. Safety Population

All subjects in the ITT population who received at least one dose of the study drug and had at least one post-Baseline safety assessment will be included in the safety population and analyzed

according to the treatment group they received. All safety analyses will be performed using the safety population.

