## **6.5 Unscheduled Study Visits**

Additional visits may be scheduled, as necessary, to ensure the safety and well-being of subjects. All additional examinations should be fully documented in the source files and eCRFs, as appropriate. Visits that fall outside the designated scheduled visit window but that are intended to fulfill scheduled visit requirements will be collected and transcribed to the appropriate scheduled visit eCRF.

If a subject is seen for multiple visits during a given visit time frame, the data from the visit(s) that are intended to meet the protocol requirements for the scheduled visit should be captured on the visit eCRF. Any other data from any additional visits within a scheduled visit interval will be captured elsewhere on the eCRF.

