### **10.4.4 Safety Population**

The safety population will include all randomized subjects who received at least one dose of study drug and had at least one post-Baseline safety assessment.

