6.1.3. Visit Mapping

Data will be summarized based on nominal visit indications with the exception of data captured at early termination and unscheduled visits. Data from early termination and unscheduled visits will be summarized based on mapped visit values. The analysis windows for early termination and unscheduled visits are presented in the following table.

Analysis Windows for Efficacy and Safety Assessments

Scheduled Visit	Target Study Day	Analysis Window (Days)
Day 8	8	4 to 11

Day 15	15	12 to 18
Day 22	22	19 to 30

Data collected at early termination and unscheduled visits prior to study day 4 will not be analyzed, with the exception of those identified as baseline values. Data collected at early termination and unscheduled visits after study day 30 will not be included in the analyses.

The definition for the study day included in each analysis window is defined as below:

Study Day prior to Baseline Visit = Visit Date – Baseline Visit Date

Study Day on or after Baseline Visit = Visit Date – Baseline Visit Date + 1

If an assessment's mapped visit is a visit at which the subject has data from a scheduled visit, or if no analyses are planned for the assessment at the mapped visit, the data collected at the early termination or unscheduled visit will not be included in analyses.

In the event of multiple values from unscheduled or early termination assessments within an analysis window, the value closest to the scheduled visit target study day will be used for analyses. If two values tie as closest to the time point (for example, one value is before and the other value is after the time point), then the later value will be selected.

Data collected at all visits will be included in the data listings with visit presented as reported by the site.

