Number of Subjects Included in the MITT Population	xx (xx.x%)	xx (xx.x%)	xx (xx.x%)
Number of Subjects Excluded from the Safety Population	xx (xx.x%)	xx (xx.x%)	xx (xx.x%)
Number of Subjects Included in the Safety Population	xx (xx.x%)	xx (xx.x%)	xx (xx.x%)
Number of Subjects Excluded from the PP Population	xx (xx.x%)	xx (xx.x%)	xx (xx.x%)
Number of Subjects Included in the PP Population	xx (xx.x%)	xx (xx.x%)	xx (xx.x%)

SOURCE: USERNAME\SPONSOR\PROJECT\JOBNAME (DATE,TIME)

Table 14.0.2: Summary of Subjects Excluded from Analyses
 (Randomized Subjects)

	7-Day Miconazole Oil (N=xx)	14-Day Miconazole Oil (N=xx)	14-Day Vehicle Oil (N=xx)
Number of Subjects Excluded from the ITT Population	xx (xx.x%)	xx (xx.x%)	xx (xx.x%)
Reason for Exclusion from the ITT Population			
Not Dispensed Study Drug	xx (xx.x%)	xx (xx.x%)	xx (xx.x%)
Number of Subjects Excluded from the MITT Population	xx (xx.x%)	xx (xx.x%)	xx (xx.x%)
Reason for Exclusion from the MITT Population			
Not Dispensed Study Drug	xx (xx.x%)	xx (xx.x%)	xx (xx.x%)
No Positive Otomycosis Diagnosis	xx (xx.x%)	xx (xx.x%)	xx (xx.x%)
Number of Subjects Excluded from the Safety Population	xx (xx.x%)	xx (xx.x%)	xx (xx.x%)
Reason for Exclusion from the Safety Population			
Not Dispensed Study Drug	xx (xx.x%)	xx (xx.x%)	xx (xx.x%)
No Post Baseline Assessment	xx (xx.x%)	xx (xx.x%)	xx (xx.x%)
Number of Subjects Excluded from the PP Population	xx (xx.x%)	xx (xx.x%)	xx (xx.x%)
Reason for Exclusion from the PP Population			
Not Dispensed Study Drug	xx (xx.x%)	xx (xx.x%)	xx (xx.x%)
No Positive Otomycosis Diagnosis	xx (xx.x%)	xx (xx.x%)	xx (xx.x%)
Violated the inclusion/exclusion criteria	xx (xx.x%)	xx (xx.x%)	xx (xx.x%)
Used an interfering concomitant medication	xx (xx.x%)	xx (xx.x%)	xx (xx.x%)
Did not attend the Test of Cure Visit	xx (xx.x%)	xx (xx.x%)	xx (xx.x%)
Have not been compliant with the dosing regimen	xx (xx.x%)	xx (xx.x%)	xx (xx.x%)
Out of visit window at the Test of Cure Visit	xx (xx.x%)	xx (xx.x%)	xx (xx.x%)

SOURCE: USERNAME\SPONSOR\PROJECT\JOBNAME (DATE,TIME)

Statistical Analysis Plan

Hill Dermaceuticals, Inc. HD-MCZ-PHII-DRF062016

Version: 1

Date: 30 MAY 2019

 Table 14.0.3: Summary of Subject Treatment Completion/Discontinuation
 (Randomized Subjects)

	7-Day Miconazole Oil (N=xx)	14-Day Miconazole Oil (N=xx)	14-Day Vehicle Oil (N=xx)
Completed Study			
Yes	xx (xx.x%)	xx (xx.x%)	xx (xx.x%)
No	xx (xx.x%)	xx (xx.x%)	xx (xx.x%)
Reason for Discontinuation			
Adverse Event	xx (xx.x%)	xx (xx.x%)	xx (xx.x%)

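### The safety population depends on an undefined post-Baseline assessment, which either drops a dosed subject who never returns or does nothing; define the set by dosing alone

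*SAP*

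**What the plan says.** Protocol 10.4.4 defines the safety population as "all randomized subjects who received at least one dose of study drug and had at least one post-Baseline safety assessment". The synopsis repeats this. SAP 6.4.4 sets the same two conditions within the ITT population: "received at least one dose of the study drug and had at least one post-Baseline safety assessment will be included in the safety population". It adds: "All safety analyses will be performed using the safety population".

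The planned Table 14.0.2 counts exclusions from each population by reason. For the safety population it offers two reasons: study drug not dispensed, and "No Post Baseline Assessment".

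SAP 6.1.3 maps early-termination and unscheduled visits to analysis windows. The window table's heading names safety as well as efficacy. The text adds: "Data collected at early termination and unscheduled visits prior to study day 4 will not be analyzed", except for baseline values. Data from such visits after study day 30 are also left out. Protocol 6.5 permits these visits: "Additional visits may be scheduled, as necessary, to ensure the safety and well-being of subjects".

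**The concern.** AEs are the trial's only stated safety evaluation (protocol synopsis and section 3; SAP 4.1). The safety endpoint is the percentage of subjects with a TEAE, counted from the first dose (protocol 10.1.4, SAP 5.2). That percentage is clearest when its denominator is everyone who was dosed.

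The second condition makes membership depend on what happens after dosing. Subjects with no later contact may include some who stopped because of an immediate reaction, so the rule can select on the outcome it is meant to measure. Protocol 1.3.1 names burning, hives and rash among the known side effects of miconazole products. Section 1.3.3 admits peanut-allergic subjects to a trial of a product containing refined peanut oil, while stating that no excessive risk is expected. With small arms, one subject is visible in the percentages.

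**Working it through.** **1. Does the second condition remove anyone?** This turns on what Baseline means, and the documents use the word in two ways.

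| Meaning of Baseline | Support in the documents | Subject who reacts to the supervised first dose and never returns |
|---|---|---|
| The Day 1 visit | Protocol Table 1 labels the whole Day 1 column Screening/Baseline. SAP 6.1.3 counts study days from the Baseline visit. Table 14.0.2 has a row for this exclusion. | The Day 1 AE check belongs to Baseline. The subject has no later assessment and is excluded. |
| Before the first dose | SAP 6.1.2 takes the last available value before dosing. Protocol 3 and 6.2.1 have AEs assessed at the site after the supervised first dose, with timing recorded as before or after it. | The Day 1 post-dose check is post-Baseline. The subject is included. |

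Under the first meaning the clause can exclude a dosed reactor. Under the second it excludes nobody who completes the Day 1 check. Neither gives a reason to keep it.

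**2. Where would an excluded subject still appear?** The TEAE tables (14.3.2.x and 14.3.3.x) use the safety population, so the subject leaves both numerator and denominator. The AE listings (SAP 6.8.3) keep the event. Table 14.0.2 counts the exclusion. Table 14.0.3 is based on randomized subjects and still counts the subject under the recorded reason for discontinuation. An AE withdrawal could therefore appear in Table 14.0.3 but be missing from Table 14.3.2.2, which tabulates TEAEs leading to withdrawal in the safety population.

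**3. Is Table 14.0.2 complete?** SAP 6.4.4 also excludes a subject who was dispensed drug but took none. Neither safety row in the table covers that case.

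**4. Do the SAP 6.1.3 day limits reach AEs?** The windows are days 4–11, 12–18 and 19–30, so days 1–3 are the only days from 1 to 30 outside every window. But the section governs which visit a value is summarised under. SAP 6.8.3 defines TEAEs by onset on or after first application, and the table index contains no AE table by visit. The limits therefore probably do not touch AE counts, although no sentence says so.

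**5. Size.** The plan gives no figure to reproduce and no rate of early reactions. The number of reactors is therefore an assumption.

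- Arm size: 75 / 3 = 25, assuming 1:1:1 throughout. SAP 6.1.6 removes 7-day kits after the allocation assessment, so final sizes may differ.
- All dosed subjects kept: (k + m) / 25. Immediate reactors dropped: m / (25 − k). Here k is the number of reactors dropped and m the number of other subjects in the arm with a TEAE.

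| k | m | All dosed kept | Reactors dropped |
|---|---|---|---|
| 1 | 0 | 1/25 = 4.0% | 0/24 = 0% |
| 2 | 0 | 2/25 = 8.0% | 0/23 = 0% |
| 3 | 0 | 3/25 = 12.0% | 0/22 = 0% |
| 1 | 2 | 3/25 = 12.0% | 2/24 = 8.3% |

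For k = 1 and m = 0, the exact (Clopper–Pearson) two-sided 95% upper limit falls from 20.4% to 14.2%; for 0/24 it is 1 − 0.025^(1/24) = 14.2%. These limits only illustrate scale, since the plan calls for no intervals on safety.

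**The case against.** The strongest reply is that the SAP already settles the matter. Section 6.1.2 places Baseline before the first dose, and AEs are checked on site after that dose, so an on-site reactor qualifies and so does one who reacts on Day 2 or 3. A redundant clause biases nothing. Protocol 4.5 also requires at least three calls after a missed visit, and 6.4 asks for Test of Cure procedures at early termination where possible. This is a fair reading and may be the intended one. It does not close the point, because SAP 6.1.2 defines a baseline value rather than a post-Baseline safety assessment, and Table 14.0.2 provides a row for the exclusion. The documents also do not say whether AE information from a telephone call would count.

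A reader might go further and infer that SAP 6.1.3 discards AEs reported at unscheduled or early-termination visits before Day 4 or after Day 30, so that acute reactors vanish from the safety results. The documents do not support that. The section is a visit-mapping rule, TEAEs are counted by onset, and no AE table is by visit. SAP 6.1.3 itself sends data from all visits to the listings. AE collection runs through the Test of Cure visit (protocol 8.4), so a visit after Day 30 would mainly follow an AE already recorded. What remains is a loose table heading and an unqualified sentence.

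**Conclusion.** The point stands as a defect in the population definition. The condition is undefined. On the visit meaning it can remove a dosed reactor from the TEAE numerator and denominator; on the before-dose meaning it is redundant. The subject would not disappear altogether, because the listings, Table 14.0.2 and Table 14.0.3 remain.

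Under the assumptions of 25 per arm, one lost reactor and no other reporter, the effect is 4.0 percentage points in that arm. The number affected may be zero, and the study is descriptive, so no formal test is at risk. Confidence is high that the clause should go. The SAP 6.1.3 matter is only a clarification, since the SAP does not clearly drop AEs through it.

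**What to change.** - **Protocol 10.4.4, synopsis and SAP 6.4.4:** define the safety population as every randomized subject given one or more doses of study drug, and delete the post-Baseline condition.
- **Table 14.0.2:** replace the safety row "No Post Baseline Assessment" with *Did not receive study drug*. This also covers subjects who were dispensed drug but took none.
- **SAP 6.1.3 (secondary):** state that the windows and the before-Day-4 and after-Day-30 exclusions do not apply to AEs, which are counted by onset whatever visit they were reported at. Amend the table heading to match.

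The cost is a wording change in two documents and one table row. The downside is that dosed subjects who are never seen again enter the denominator with no reported AE, which can slightly dilute the percentages. Table 14.0.3 will still show how many subjects were lost to follow-up.

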6.5. Demographic and Other Baseline Characteristics

All demographic and baseline characteristic summaries will be done for the MITT, PP, and safety populations.

Sex, race, and ethnicity will be summarized by counts and percentages. Age will be summarized with descriptive statistics.

Baseline mycological culture, signs and symptoms of otomycosis, and subject global assessment will be summarized with descriptive statistics.

Medical histories will be coded using the Medical Dictionary for Regulatory Activities (MedDRA) dictionary and presented in a by-subject listing.

6.6. Prior and Concomitant Medications

Concomitant medications will be coded to preferred name and Anatomical Therapeutic Chemical (ATC) classification of ingredients using the World Health Organization (WHO) Drug dictionary (WHO-DDE)

Counts and percentages will be provided to summarize the use of medications other than the study drug reported throughout the study. The number and percent of subjects who took other therapy will be shown by ATC level 2 term and preferred name. Medications which start prior to first dose will be considered prior medications. Ongoing medications and medications ending after the date of first dose will be considered concomitant medications. Medications which are both prior and concomitant will be included in both summaries. Incomplete start and end dates which could be either prior to first dose or after first dose will be considered prior to first dose.

A by-subject listing of all prior and concomitant medications will be presented.

6.7. Analysis of Efficacy

6.7.1. Primary Efficacy Analysis

The primary population for all efficacy analyses will be the MITT population. Efficacy endpoints will also be summarized for the PP population and will be considered supportive.

The percentage of subjects who demonstrate a positive outcome for each efficacy endpoint will be presented for the primary efficacy parameter as well as all secondary efficacy parameters.

In cases of bilateral otomycosis, the ear with the worse infection at Screening/Baseline, as assessed by the investigator by taking into account both clinical signs and symptoms and fungal culture results, will be used as the study ear for efficacy analyses. If both ears are determined by the investigator to have the same degree of infection at Screening/Baseline, the left ear will be used as the study ear for the purposes of efficacy analyses.

The Test of Cure Visit is scheduled to occur on Day 15 for subjects randomized to the 7-day treatment duration, or on Day 22 for subjects randomized to the 14-day treatment durations.

The percentage of subjects with “therapeutic cure” at the Test of Cure Visit will be presented by treatment group. Subjects are defined as reaching “therapeutic cure” if they have a negative mycological culture plus “clinical cure” for the study ear, where “clinical cure” is defined as the absence of all otomycosis signs and symptoms based on Investigator assessment according to the scales for each individual sign or symptom and with absence defined as score of 0 on each of the scales for pruritus, debris, fungal elements, and pain.

In addition otomycosis signs and symptoms will be presented as the percentage of subjects with occurrences by treatment arm, assessor type (subject or investigator assessment), and visit. Subject assessments will be summarized for pruritus only.

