### 3 STUDY DESIGN

This study is a randomized, partially masked, multiple-dose, parallel-group design study conducted at up to 10 study centers in the US. Approximately 75 male or female subjects with otomycosis will receive study drug. Subjects will be randomly assigned in a 1:1:1 ratio to receive miconazole oil [administered as 5 drops per ear at ~30 mg per drop instilled into the external ear canal of the ear(s) affected by otomycosis] for 7 or 14 days, or vehicle for 14 days. Interim assessments are planned to ensure that there is a sufficient number of subjects within each group for the primary analysis. If deemed necessary the randomization ratio may be adjusted following the interim assessments; see [Section 10.5.5](#) for details. For subjects assigned to the 14-day treatment duration with either miconazole oil or vehicle, the contents of the study drug will be masked to both the subject and the investigator and study staff (i.e., double-blind), but the treatment duration assigned to each subject (7 or 14 days) will be unmasked to both the subject and the investigator and study staff.

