8. For subjects with only one ear meeting all study eligibility criteria, the subject will be eligible for the study, and the ear meeting all eligibility criteria will be treated with study drug and considered to be the study ear for the purposes of study evaluations. In case of bilateral otomycosis in which both ears meet all study eligibility criteria, the subject will be eligible for the study, both ears may be treated with study drug, and the worse ear will be considered to be the study ear for the purposes of study evaluations. If both ears meet study eligibility criteria and are determined by the investigator to have the same degree of infection at Screening/Baseline, the left ear will be considered to be the study ear for the purposes of study evaluations.

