## 4.4 Subject Discontinuation

A subject MAY be withdrawn from the study (at the discretion of the investigator, sponsor, and/or IRB) prior to study completion for any of the following reasons, including, but not limited to:

- A serious adverse event (SAE) occurring during the course of the study which precludes continued follow-up
- Intercurrent illness which may, in the investigator's opinion, significantly affect study assessments
- Failure to follow required study procedures

A subject MUST be discontinued prior to the final study visit for any of the following reasons:

- Whenever the subject decides it is in his/her best interest to withdraw
- Whenever the investigator decides it is in the subject's best interest to be withdrawn

Prior to discontinuing a subject, every effort should be made to contact the subject, schedule a final study visit, and obtain as much follow-up data as possible. If possible, the assessment schedule for the Test of Cure Visit should be performed, and an effort should be made to collect all study drug.

Due to the time required to obtain fungal culture results from Screening/Baseline, subjects will be enrolled into the study based on a clinical diagnosis of otomycosis (including the visible presence of fungal elements at Screening/Baseline), without a requirement for a positive fungal culture. Subjects who end up with a negative Screening/Baseline fungal culture will not be discontinued from the study, but these subjects will not be included in the primary efficacy analysis. Because the sponsor's goal is to obtain approximately 10 subjects per group who meet both criteria of having a positive fungal culture at Screening/Baseline and completing the Test of Cure Visit, the number of subjects enrolled into the study may be adjusted depending on the rates of negative fungal culture at Screening/Baseline and of discontinuation or loss to follow-up.

Subject discontinuations will be documented clearly on the applicable electronic case report form (eCRF). Subjects who discontinue from the study will not be replaced, but additional subjects may be enrolled and randomized if it appears that approximately 75 subjects is insufficient to meet the sponsor's goal of approximately 10 subjects per group who meet both criteria of having a positive fungal culture at Screening/Baseline and completing the Test of Cure Visit.

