#### 9.1.1 Administration

Subjects will be seated or lying on one side with the head positioned so the ear being treated is facing up. If both ears are being treated, the ear that appears to have less severe disease will be treated first. The subject or caregiver will gently pull the ear lobe backward and upward and apply 5 drops of miconazole oil into the ear. The subject will be instructed to keep the head positioned with the ear facing up for approximately 1 minute to allow the miconazole oil to coat the ear canal. After 1 minute, the subject can then straighten his/her head, and excess material dripping out of the ear can be gently patted using a clean cotton ball.

If both ears are being treated, the subject will then wait at least 5 minutes, then repeat this procedure for the second ear.

While on study treatment, subjects will be instructed to avoid getting water in the ear, to consider drying excessive water in the ear by using a blow dryer, and to place a Vaseline-impregnated cotton ball over the affected ear(s) to help keep water out of the ear(s) while bathing or showering. Subjects will be asked to avoid bathing or shower for at least 30 minutes after applying study drug.

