6.1.6. Interim Analyses and Data Monitoring

An interim assessment of the treatment allocation will be performed to ensure that there is a sufficient number of subjects within and across treatment arms. A subject's MITT status (specifically positive fungal culture at baseline) is determined only after randomization which may result in an imbalance between treatment groups. Therefore, at least one assessment during the conduct of the study is planned to ensure that there is a sufficient number of subjects within each group for the primary analysis. Once at least 10 MITT subjects have been enrolled in the 7-Day active group, the numbers of MITT subjects in the 14-Day active group and the 14-Day

vehicle group will be determined by an unblinded statistician; no persons involved in the day to day conduct of the study will be unblinded. Randomization allocation for future subjects may be adjusted if deemed necessary to achieve minimum number of subjects within each arm. At the time of the assessment, the 7-Day active kits will be removed from the randomization schedule for future subjects and the table below will be used as a guide for adjustments to the randomization allocation of 14-Day kits for future subjects. This assessment may be repeated in order to ascertain that a minimum enrollment of MITT subjects is met for each treatment group before study end.

14-Day Active	14-Day Vehicle	Action
$\geq e + 3$	$\leq e - 3$	Skip 14-Day Active kits
$\geq e + 2$	$e - 2$	Skip 14-Day Active kits with the exception of one kit at each site. One of the four lowest 14-Day Active kit numbers will be selected at random to remain in the schedule for each site.
$e - 1$ to $e + 2$	$e - 1$ to $e + 2$	No action
$e - 2$	$\geq e + 2$	Skip 14-Day Vehicle kits with the exception of one kit at each site. One of the four lowest 14-Day Active kit numbers will be selected at random to remain in the schedule for each site.
$\leq e - 3$	$\geq e + 3$	Skip 14-Day Vehicle kits

Note: e represents the expected number of subjects based on a 1:1 ratio and the current number of MITT subjects between the 14-Day active and 14-Day vehicle groups. $e = \frac{1}{2} * (\text{Current number of MITT subjects between the 14-Day groups})$, non-integer results will be rounded down to the nearest integer. When determining an action the conditions of both the 14-Day Active and 14-Day Vehicle columns must be met.

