10. INDEX OF PLANNED LISTINGS

Listing 16.1.7: Randomization Scheme	81
Listing 16.2.1.1: End of Study Information	82
Listing 16.2.1.2: Discontinued Subjects	83
Listing 16.2.1.3: Screen Failures	84
Listing 16.2.2.1: Inclusion/Exclusion Criteria Violations	85
Listing 16.2.3: Analysis Populations	86
Listing 16.2.4.1: Subject Demographic Information	87
Listing 16.2.4.2.1: Unique Medical History Coded to MedDRA System Organ Classes and Preferred Terms	88
Listing 16.2.4.2.2: Medical History	89
Listing 16.2.4.3: Physical Examination	90
Listing 16.2.4.3.1: Unique Medication Names Coded to WHO-DDE ATC Level 2 Terms and Preferred Names	91
Listing 16.2.4.3.2: Prior and Concomitant Medications	92
Listing 16.2.4.4: Prior and Concomitant Procedures/Therapies	93
Listing 16.2.5.1: Study Visit Compliance	94
Listing 16.2.5.2: Subject Dosing Compliance	95
Listing 16.2.5.3: Missed/Extra Doses	96
Listing 16.2.5.4: Study Drug Dispensing and Return	97
Listing 16.2.6.1: Otomycosis Signs and Symptoms	98
Listing 16.2.6.2: Subject Global Assessment	99
Listing 16.2.7.2.1: Unique Adverse Events Coded to MedDRA System Organ Classes and Preferred Terms	100
Listing 16.2.7.2.2: Pre-Treatment Adverse Events	101
Listing 16.2.7.2.3: Treatment-Emergent Adverse Events	102
Listing 16.2.7.2.4: Serious Adverse Events	103
Listing 16.2.8.1.1: Urine Pregnancy Test Results	104
Listing 16.2.8.2.1: Microbial Culture Results	105

Listing 16.1.7: Randomization Scheme
 (Page xx of yy)

Subject	Age/Sex	Eval	Randomization Date	Assigned Arm	Treated Ear(s)	Worse Ear
xxxxxx	xxxx	xxxxxxxxxx	xxxxxxxxxx	xxxxxxxx xxxxxx	xxxx	xxx xxxx xxxx xxxx xxxxx xxxxxxxxx
xxxxxx	xxxx	xxxxxxxxxx	xxxxxxxxxx	xxxxxxxx xxxxxx	xxxxx	
xxxxxx	xxxx	xxxxxxxxxx	xxxxxxxxxx	xxxxxxxx xxxxxx	xxxx	

SOURCE: USERNAME\SPONSOR\PROJECT\JOBNAME (DATE, TIME)

Listing 16.2.1.1: End of Study Information
 Treatment Arm
 (Page xx of yy)

Subject	Age/Sex	Eval	Date of First Dose of Study	Date of Last Dose of Study Drug	Reason for End of Treatment	Reason for Study Completion/Discontinuation	Date of Study Completion/Discontinuation (Day) ¹
xxxxxx	xxxx	xxxxxxxxxx	xxxxxxxxxx	xxxxxxxxxx	xxxxxxxxxx	xxxxxxxxxx	xxxxxxxxxx xxxx
xxxxxx	xxxx	xxxxxxxxxx	xxxxxxxxxx	xxxxxxxxxx	xxxxxxxxxx	xxxxxxxxxx	xxxxxxxxxx xxxx
xxxxxx	xxxx	xxxxxxxxxx	xxxxxxxxxx	xxxxxxxxxx	xxxxxxxxxx	xxxxxxxxxx	xxxxxxxxxx xxxx
xxxxxx	xxxx	xxxxxxxxxx	xxxxxxxxxx	xxxxxxxxxx	xxxxxxxxxx	xxxxxxxxxx	xxxxxxxxxx xxxx
xxxxxx	xxxx	xxxxxxxxxx	xxxxxxxxxx	xxxxxxxxxx	xxxxxxxxxx	xxxxxxxxxx	xxxxxxxxxx xxxx

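### In bilateral cases a culture-based choice of study ear can be completed only after treatment duration is known, and MITT does not require the positive culture to be in that ear

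*SAP*

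**What the plan says.** **Which ear is scored.** When both ears are treated, SAP 6.7.1 makes the worse ear at baseline the study ear, "as assessed by the investigator by taking into account both clinical signs and symptoms and fungal culture results", and the left ear if the two are equal. The same rule stands in the Protocol Synopsis, Sections 3 and 10.5.1, and in SAP Sections 2 and 4.1. Protocol 4.1, criterion 8, says "the worse ear will be considered to be the study ear for the purposes of study evaluations" and does not mention culture.

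**When culture is known.** Protocol 4.4: "Due to the time required to obtain fungal culture results from Screening/Baseline, subjects will be enrolled into the study based on a clinical diagnosis". SAP 6.1.6: a subject's "MITT status (specifically positive fungal culture at baseline) is determined only after randomization". Signs and symptoms, by contrast, are scored on Day 1 before randomisation (Protocol 6.2.1). The dosing instructions already need a clinical ranking of the ears, since "the ear that appears to have less severe disease will be treated first" (Protocol 9.1.1).

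**Who knows what.** Protocol 3: "the treatment duration assigned to each subject (7 or 14 days) will be unmasked to both the subject and the investigator and study staff". Active versus vehicle within the 14-day groups is masked (Protocol 9.3, SAP 4.1.3).

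**How the choice is recorded.** SAP 6.2 tabulates the treated ear "as well as an indication of worse ear if" both are treated. "Listing 16.1.7: Randomization Scheme" has columns for randomisation date and worse ear, but none for the date of the choice.

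**Who is analysed.** MITT (Protocol 10.4.2, SAP 6.4.2) needs a clinical diagnosis confirmed by a positive fungal culture; neither definition names an ear. Both treated ears are cultured (Protocol 7.6), and therapeutic cure is scored on the study ear (Protocol 10.1.1, SAP 6.7.1).

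**The concern.** There are two gaps, and both touch bilateral subjects only.

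First, a ranking that weighs culture cannot be finished on Day 1. When the result arrives, the investigator already knows who is in the 7-day arm. No weighting, deadline or locking step is given, so the plan permits a discretionary choice of analysis ear after allocation. What is at stake is the 7- versus 14-day comparison, one of the two study objectives.

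Second, a subject can enter MITT on the strength of one ear and be scored on the other. A study ear that is culture-negative at baseline starts out with the culture component of therapeutic cure already satisfied. It cannot show a mycological response. This can happen in any arm, so it also bears on the vehicle comparison. The PP population is a subset of MITT and inherits the problem. MITT counts also trigger and steer the allocation adjustment in SAP 6.1.6, so the definition should be unambiguous.

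**Working it through.** **The plan's own figure.** Protocol 3.1 plans about 75 enrolled to reach about 10 evaluable per group: 75/3 = 25 per arm and 30/75 = 40% implied yield. No basis for that yield is stated, so it can be read off but not reproduced. One subject in 10 is 10 percentage points.

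**Timing, side by side.** Signs: Day 1, before randomisation. Culture: after randomisation. Duration: known to the investigator from allocation. Contents: masked in the 14-day groups. A choice on signs alone can precede allocation; one that uses culture cannot. The two planned comparisons (Protocol 10.2) are 14-day active versus vehicle, where the investigator cannot tell the arms apart, and 7 versus 14 days, where the investigator can. Only the second is exposed to knowledge of arm. How often a choice is made late cannot be sized from the documents.

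**Effect of the MITT gap.** Let q be the share of MITT subjects whose study ear is culture-negative at baseline, and m the arm's rate of positive ears turning negative. If the q ears stay negative:

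- arm rate = q × 1 + (1 − q) × m = m + q(1 − m), a rise of q(1 − m);
- difference between arms with the same q = (1 − q)(m₁ − m₂).

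The rise is not equal across arms. At q = 0.03 it is 0.03 × 0.7 = 2.1 points where m = 0.3, and 0.03 × 0.3 = 0.9 points where m = 0.7. The 40-point difference becomes 40 × 0.97 = 38.8.

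**Ceilings for q.** The documents give neither the bilateral share b nor the between-ear agreement, so the following are assumptions. Let p be the per-ear positive rate and r the between-ear correlation. Among bilateral subjects with any positive ear, the share positive in one ear only is s = D/(D + B), with D = 2p(1 − p)(1 − r) and B = p² + r·p(1 − p). If culture were ignored in choosing the ear, half of these would have a negative study ear: q = b × s × 0.5.

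| Case | b | p, r | s | q | Expected per 10 | Chance of at least one in 10, 1 − (1 − q)¹⁰ | Rise q(1 − m) | A 40-point difference becomes |
|---|---|---|---|---|---|---|---|---|
| Low | 5% | 0.6, 0.8 | 0.096/0.648 = 14.8% | 0.0037 | 0.04 | 4% | 0.1 points (m = 0.7) | 39.9 |
| Middle | 15% | 0.5, 0.5 | 0.25/0.625 = 40% | 0.030 | 0.30 | 26% | 1.5 points (m = 0.5) | 38.8 |
| High | 30% | 0.4, 0 | 0.48/0.64 = 75% | 0.1125 | 1.1 | 70% | 7.9 points (m = 0.3) | 35.5 |

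Each row is an upper figure for its assumptions, because the stated rule does count culture. The effect on therapeutic cure is smaller, since all four signs and symptoms must also score 0.

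**Effect on one realised arm.** Suppose an arm has 5 of 10 cured, and one of the 10 has a culture-negative study ear. Excluding that subject gives 4/9 = 44.4% if the subject was cured, or 5/9 = 55.6% if not. The exact 95% interval for 5/10 is 18.7% to 81.3%.

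**The case against.** The strongest reply is that the two gaps pull against each other. If culture is used, a culture-negative study ear is unlikely. If the ear is fixed on Day 1 without culture, nothing is decided after allocation. Criterion 8 supports the Day 1 reading: it is an eligibility criterion, eligibility is determined before randomisation, and every version of the rule refers to the state of the ears at baseline. The eCRF, where the choice would be recorded, is not among the documents. Table 14.1.2.1 shows baseline culture by arm for the study ear only, so any culture-negative study ear in MITT would be visible. The study is descriptive, and sampling error exceeds every effect in the table.

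Much of this stands, and it limits the size of the point. It does not remove it. Used culture leaves the first gap, unused culture widens the second, and culture that is used but outweighed by signs leaves both. Criterion 8 and SAP 6.7.1 differ on whether culture enters the ranking at all, and that difference decides the timing. The table would reveal the problem but does not prevent it.

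Some stronger readings are tempting but not supported:

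- A reader might infer that allocation is open throughout. Only duration is; the vehicle comparison is protected from ear choice driven by knowledge of arm.
- A reader might infer that investigators do choose the ear late, or after seeing outcomes. The documents permit a late choice but do not show one.
- A reader might infer that the MITT gap lifts all arms alike. By q(1 − m), the arm with the lower conversion rate rises more.
- A reader might take the Negative row in the MITT baseline table as evidence that such ears are expected. The same shell serves the Safety population, where negative cultures are routine, so the row shows only that the case is not ruled out.

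**Conclusion.** The point holds in limited form and should be fixed. As written, the plan lets an investigator who knows treatment duration complete the choice of study ear after allocation, which exposes the 7- versus 14-day comparison only. It also lets a bilateral subject with a culture-negative study ear into the primary analysis in any arm.

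The size is unknown because the bilateral share is not stated. On the assumptions above, with culture ignored, the ceiling runs from 0.04 to 1.1 such subjects per 10, and a 40-point difference in negative-culture rate would shrink to between 39.9 and 35.5. The shrinkage figures assume equal q across arms and ears that stay negative. The true q is probably small, because the rule does count culture. The practical reason to act is that one subject is worth 10 points at about 10 per group.

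**What to change.** 1. **MITT.** State in Protocol 10.4.2 and SAP 6.4.2 that the positive Screening/Baseline fungal culture must be in the study ear. Carry this into the Synopsis definition and SAP 6.1.9.

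2. **Study ear.** Reconcile criterion 8 with the Synopsis, Protocol 3 and 10.5.1, and SAP 2, 4.1 and 6.7.1. Fix the ear by a pre-specified rule that uses only data collected before the first dose and leaves no discretion after allocation. One example:
   - if exactly one treated ear is culture-positive at baseline, it is the study ear;
   - otherwise, take the ear ranked clinically worse and recorded before randomisation;
   - if tied, take the left ear.

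   State what happens if one ear's culture is missing. The severity score is the sponsor's choice, but the fungal-elements score cannot separate the ears: it is 0/1, and eligibility requires it above 0 in every treated ear.

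Where both cultures are available, the example rule means that change 1 loses no subject compared with counting a positive culture in either ear.

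**Cost.** SAP edits and minor programming. The protocol passages need an amendment with FDA submission and IRB approval (Protocol 7.12). No new data are needed: signs and cultures are already listed by ear (Listings 16.2.6.1 and 16.2.8.2.1). The downside is that under the example rule the study ear may sometimes be the clinically milder one, so the description of the worse ear must be reworded to match.
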